6. IBRUTINIB

Ibrutinib is a first-in-class, potent, orally administered covalently-binding inhibitor of Bruton's tyrosine kinase (BTK) and interleukin-2-inducible kinase (ITK). Inhibition of BTK blocks downstream BCR signaling pathways and thus prevents B-cell proliferation. In vitro, ibrutinib inhibits purified BTK and selected members of the kinase family with 10-fold specificity compared with non-BTK kinases. Ibrutinib (IMBRUVICA™) is approved by the U.S. Food and Drug Administration (FDA) for the treatment of patients with the following conditions:

- Mantle cell lymphoma (MCL) who have received at least one prior therapy. Accelerated approval was granted for this indication based on overall response rate. Continued approval for this indication may be contingent upon verification and description of clinical benefit in a confirmatory trial.
- Chronic lymphocytic leukemia (CLL)/Small lymphocytic lymphoma (SLL)
- Chronic lymphocytic leukemia (CLL)/Small lymphocytic lymphoma (SLL) with 17p deletion
- Waldenström's macroglobulinemia (WM)
- Marginal zone lymphoma (MZL) who require systemic therapy and have received at least one prior anti-CD20-based therapy Accelerated approval was granted for this indication based on overall response rate. Continued approval for this indication may be contingent upon verification and description of clinical benefit in a confirmatory trial.
- Chronic graft versus host disease (cGVHD) after failure of one or more lines of systemic therapy

6.1 Summary of Non-Clinical Data

For the most comprehensive nonclinical and clinical information regarding ibrutinib background, safety, efficacy, and in vitro and in vivo preclinical activity and toxicology of ibrutinib, refer to the latest version of the ibrutinib USPI.

6.2 Data on Use of Ibrutinib Post-HCT

NCT02195869 investigated the role of single agent ibrutinib in patients post HCT for established steroid-refractory or dependent chronic GVHD, and a dose of 420 mg orally once a day was established as the recommended dose for chronic GVHD.

Ibrutinib has been used post HCT for CLL and MCL for management of recurrent disease. Coutre et al reported on 16 patients who had received an HCT prior to ibrutinib in studies 1102, 1109, 1112 and 1117 were pooled to consolidate the experience of treating patients with Ibrutinib after HCT failure. Median time since the most recent HCT was 27 months (range, 8-115). Best overall response rate (ORR) was 87.5% and was consistent with results observed in the overall /broader population. The authors concluded that Ibrutinib was well tolerated in patients who had prior HCT, with a safety profile similar to that observed in the overall R/R CLL population. They also presented a case showing a patient who achieved donor chimerism (i.e. full acceptance of the donor B Cells) following ibrutinib treatment, achieved MRD-ve disease and then interrupted for 10 months without relapse to date³⁶.

Ryan et al reported on 5 patients with CLL relapsing after HCT who were treated with Ibrutinib. All patients responded and 2 patients (11q and 17p) have returned to MRD negative status. Three patients

have achieved donor chimerism. In addition, there was symptomatic improvement in oral and skin chronic GVHD³⁷.

To date, ibrutinib shows clinically meaningful efficacy with a tolerable safety profile. For additional information, please see the text below, as well as the USPI and Investigator's Brochure.

6.3 Drug Information

6.3.1 Pharmacology

Ibrutinib is a small-molecule inhibitor of BTK and ITK. Ibrutinib is a white to off-white solid, and its molecular formula is C₂₅H₂₄N₆O₂ and molecular weight is 440.50 g/mole. Both tablet and capsule forms are available, and the results of bioequivalence studies may be found in the Investigator's Brochure. Ibrutinib forms a covalent bond with a cysteine residue (Cys-481) in the BTK active site, leading to inhibition of BTK enzymatic activity; ibrutinib also binds irreversibly to the equivalent cysteine in the ITK pocket. BTK is a signaling molecule of the B-cell antigen receptor (BCR) and cytokine receptor pathways. BTK's role in signaling through the B-cell surface receptors results in activation of pathways necessary for B-cell trafficking, chemotaxis, and adhesion. Nonclinical studies show that ibrutinib inhibits malignant B-cell proliferation and survival *in vivo* as well as cell migration and substrate adhesion *in vitro* (refer to the current USPI and Investigator's Brochure).

Ibrutinib was designed as a selective and covalent inhibitor of BTK (Pan 2007). *In vitro*, ibrutinib is a potent inhibitor of BTK activity (IC₅₀ = 0.39 nM). The irreversible binding of ibrutinib to cysteine-481 in the active site of BTK results in sustained inhibition of BTK catalytic activity and enhanced selectivity over other kinases that do not contain a cysteine at this position. When added directly to human whole blood, ibrutinib inhibits signal transduction from the B-cell receptor and blocks primary B-cell activation (IC₅₀ = 80 nM) as assayed by anti-IgM stimulation followed by CD69 expression (Herman 2011).

For comprehensive information regarding the nonclinical pharmacology and toxicology of ibrutinib, please refer to the current USPI and Investigator's Brochure.

6.3.2 Clinical Pharmacology of Ibrutinib

For the most comprehensive clinical pharmacology information regarding ibrutinib, please refer to the current version of the USPI and the Investigator's Brochure.

6.3.3 Summary of Clinical Safety Data

As of 12 November 2019, ibrutinib has been studied as both a monotherapy and combination therapy in 53 completed (primary or final analyses) and 17 ongoing company-sponsored studies, 9 early access programs (ongoing or completed), and 175 investigator-initiated studies (ongoing or completed). Safety data for completed studies is available for 4,439 subjects, of which, 2,132 were treated with ibrutinib monotherapy (1,600 subjects with hematologic malignancies, 42 subjects with cGVHD, 460 healthy

volunteers, and 30 subjects in a hepatic impairment study). Ibrutinib has been approved in approximately 100 countries for 1 or more indications.

Treatment-emergent AEs and adverse events leading to treatment discontinuation were assessed by performing an integrated analysis of 1600 subjects with hematologic malignancies treated with ibrutinib monotherapy.

Treatment-emergent AEs were observed in 98.8% of subjects taking ibrutinib monotherapy; 86.4% of subjects experienced AEs that were considered to be related to ibrutinib treatment by the assessing investigator. Grade 3 or 4 and serious AEs were experienced by 70.8%, and 52.9% of subjects, respectively, and fatal AEs were reported in 9.9% of subjects.

Treatment-emergent adverse events (observed in >20% of patients) that were considered by the investigator to be related to ibrutinib use were:

- Diarrhea
- Fatigue

The most commonly reported Grade 3 or 4 treatment-emergent AEs (observed in >5% of patients) were:

- Neutropenia
- Pneumonia
- Thrombocytopenia
- Anemia
- Hypertension

The most common serious treatment-emergency AEs (observed in >2% of patients) were:

- Pneumonia
- Atrial fibrillation
- Pyrexia
- Febrile neutropenia
- Sepsis
- Cellulitis

Treatment-emergent AEs that most commonly resulted in death (excluding disease progression) were:

- Pneumonia
- Sepsis
- Richter's syndrome
- Respiratory failure
- Cardiac arrest
- Death (unspecified)

16.8% of patients discontinued ibrutinib due to a treatment-emergent AE. Treatment-emergent AEs that most often lead to discontinuation were:

- Pneumonia (1.7%)
- Sepsis (0.8%)
- Thrombocytopenia (0.7%)
- Subdural hematoma (0.6%)

Treatment-emergent AEs in patients with cGVHD, steroid-dependent or refractory, were similar to those observed in patients with hematologic malignancies. The median and mean duration of ibrutinib treatment was 4.4 months and 9.1 months, respectively. Data from 47 patients was included in the analysis, and all patients were taking ibrutinib in combination with prednisone.

Treatment-emergent adverse events (observed in >20% of patients) that were considered by the investigator to be related to ibrutinib use were:

- Diarrhea
- Fatigue

The most commonly reported Grade 3 or 4 treatment-emergent AEs (observed in >5% of patients) were:

- Pneumonia
- Fatigue
- Diarrhea
- Cellulitis
- Hyperglycemia
- Hypokalemia

The most common serious treatment-emergency AEs (observed in >2% of patients) were:

- Pneumonia
- Cellulitis
- Dyspnea
- Headache
- Septic Shock

Fatal treatment-emergent AEs were observed in 2 subjects (4.8%): bronchopulmonary aspergillosis (considered related) and pneumonia (considered unrelated).

42.9% of patients (18 subjects) discontinued ibrutinib due to at least 1 treatment-emergent AE. The most common treatment-emergent AEs that led to discontinuation were:

- Fatigue (4.8%)
- Pneumonia (4.8%)

For additional information on the clinical safety of ibrutinib, refer to the ibrutinib Investigator's Brochure.

6.4 Formulation/Packaging/Storage

The white opaque 140 mg and 70 mg capsules marked with "ibr 140 mg" or "ibr 70 mg" respectively in black ink are available in white HDPE bottles with a child-resistant closure:

Store bottles at room temperature 20°C to 25°C (68°F to 77°F). Excursions are permitted between 15°C and 30°C (59°F to 86°F). Retain in original package until dispensing.

6.5 Dose and Administration

Ibrutinib will be administered at a dose of 420 mg by mouth once a day starting between day 60-90 post HCT and continue until 1y post HCT. Ibrutinib is dispensed as 140 mg capsules and patients will be

instructed to take 3 capsules by mouth once a day. Patients will be instructed to take the drug at approximately the same time every day. Patients will be instructed to swallow the capsules whole with water and not to open, break or chew the capsules.

If a dose of ibrutinib is not taken at the scheduled time, it can be taken as soon as possible on the same day with a return to the normal schedule the following day. Extra capsules of ibrutinib should not be taken to make up for the missed dose.

For patients on azoles, the starting dose will be 140 mg by mouth once a day starting between day 60-90 post HCT and continue until 1y post HCT.

Patients using Posaconazole as outlined in section 11.2 will start ibrutinib at a dose of 70 mg by mouth once a day between day 60-90 post HCT and continue until 1 year post HCT.

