	
 ● Prior to administration of ibrutinib (day 60 to day 90 post SCT) 
 ○ In the critical care unit, or use of mechanical ventilation or use of renal replacement therapy at any time post SCT and prior to administration of ibrutinib ○ Active uncontrolled stage 3-4 acute GI GVHD prior to administration of ibrutinib ○ Active uncontrolled stage 4 acute liver GVHD prior to administration of ibrutinib ○ Evidence of progressive disease as compared to pre-SCT (persistence of disease is permitted) ○ Anticipated planned donor lymphocyte infusion in the first 3 months post-SCT ○ Active uncontrolled bacterial or invasive fungal infections ○ Prednisone equivalent of >2mg/kg for treatment of GVHD prior to administration of ibrutinib ○ Use of second line systemic therapy for treatment of acute GVHD prior to administration of ibrutinib ○ Any life-threatening illness, medical condition, or organ system dysfunction which, in the investigator's opinion, could compromise the subject's safety, interfere with the absorption or metabolism of ibrutinib capsules, or put the study outcomes at undue risk including the presence of chronic/active HBV and HBC infections and Child-Pugh Class C. ○ Major surgery or a wound that has not fully healed within 4 weeks of starting ibrutinib ○ Requires anticoagulation with warfarin or equivalent vitamin K antagonists (e.g., phenprocoumon). ○ Requires chronic treatment with strong CYP3A inhibitors ○ Vaccinated with live, attenuated vaccines within 4 weeks of starting ibrutinib

Study schedule
	
Patients will start ibrutinib at a dose of 420 mg by mouth once a day between day 60-90 post HCT and continue until 1 y post HCT.
 
Patients on azoles will start ibrutinib at a dose of 140 mg by mouth once a day between day 60-90 post HCT and continue until 1 year post HCT.
 
Patients using Posaconazole as outlined in section 11.2 will start ibrutinib at a dose of 70 mg by mouth once a day between day 60-90 post HCT and continue until 1 year post HCT.

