11.2 Dose Modifications for Use with CYP3A Inhibitors

Avoid co-administration with strong or moderate CYP3A inhibitors and consider alternative agents with less CYP3A inhibition.

Concomitant use of strong CYP3A inhibitors which would be taken chronically (e.g., ritonavir, indinavir, nelfinavir, saquinavir, boceprevir, telaprevir, nefazodone) is not recommended. For short-term use (treatment for 7 days or less) of strong CYP3A inhibitors (e.g., antifungals and antibiotics) consider interrupting IMBRUVICA therapy until the CYP3A inhibitor is no longer needed.

Reduce IMBRUVICA dose to 140 mg if a moderate CYP3A inhibitor must be used (e.g., fluconazole, darunavir, erythromycin, diltiazem, atazanavir, aprepitant, amprenavir, fosamprevir, crizotinib, imatinib, verapamil, and ciprofloxacin).

Patients taking concomitant strong or moderate CYP3A inhibitors should be monitored more closely for signs of IMBRUVICA toxicity.

As most post-HCT patients are expected to be on azoles (fluconazole, voriconazole or lower doses of posaconazole as outlined in the table below) until day 100 after HCT, the dose of IMBRUVICA will be 140 mg per day. For patients receiving higher doses of posaconazole as outlined below, the dose of IMBRUVICA will be 70 mg per day. Once these agents are stopped, the dose will be escalated to 420 mg per day.

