2.4 Dose Modifications for Use with CYP3A Inhibitors		
Recommended dose modifications are described below [see Drug Interactions (7.1)]:		
Patient Population	Coadministered Drug	Recommended IMBRUVICA Dose
B-Cell Malignancies	
 Moderate CYP3A inhibitor Voriconazole 200 mg twice daily Posaconazole suspension 100 mg once daily, 100 mg twice daily, or 200 mg twice daily 	140 mg once daily Interrupt dose as recommended [see Dosage and Administration (2.3)].
	
 Posaconazole suspension 200 mg three times daily or 400 mg twice daily Posaconazole IV injection 300 mg once daily Posaconazole delayed-release tablets 300 mg once daily 	70 mg once daily Interrupt dose as recommended [see Dosage and Administration (2.3)].
	
 Other strong CYP3A inhibitors 	Avoid concomitant use. If these inhibitors will be used short-term (such as anti-infectives for seven days or less), interrupt IMBRUVICA.

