13.2 Medications to be Used with Caution

CYP3A Inhibitors/Inducers

Concomitant use of ibrutinib and drugs that strongly or moderately inhibit CYP3A can increase ibrutinib exposure, and strong CYP3A inhibitors should be avoided. In healthy volunteers, co-administration of ketoconazole, a strong CYP3A inhibitor, increased C_{max} and AUC of ibrutinib by 29- and 24-fold, respectively.

Voriconazole and posaconazole can be used concomitantly with ibrutinib, with dose modifications as described above in Section 11.2.

Strong inhibitors of CYP3A (eg, ketoconazole, indinavir, nelfinavir, ritonavir, saquinavir, clarithromycin, telithromycin, itraconazole, nefazodone, and cobicistat) should be avoided, and an alternative with less CYP3A inhibitory potential should be considered.

For strong CYP3A inhibitors used short-term (e.g., antifungals and antibiotics for 7 days or less, e.g., ketoconazole, itraconazole, voriconazole, posaconazole, clarithromycin, telithromycin) consider interrupting IMBRUVICA therapy during the duration of inhibitor use.

Concomitant use of strong CYP3A inhibitors which would be taken chronically (e.g., ritonavir, indinavir, nelfinavir, saquinavir, boceprevir, telaprevir, nefazodone) is not recommended.

Patients taking concomitant strong or moderate CYP3A4 inhibitors should be monitored more closely for signs of IMBRUVICA toxicity. Avoid grapefruit and Seville oranges during IMBRUVICA treatment, as these contain moderate inhibitors of CYP3A.

Administration of ibrutinib with strong inducers of CYP3A decreases ibrutinib plasma concentrations by up to 90%. Avoid concomitant use of strong CYP3A inducers (e.g., carbamazepine, rifampin, phenytoin and St. John's Wort). Consider alternative agents with less CYP3A induction.

A comprehensive list of inhibitors, inducers, and substrates may be found at <http://medicine.iupui.edu/clinpharm/ddis/table.aspx>. This website is continually revised and should be checked frequently for updates.

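### The 140 mg starting dose for unnamed azoles in Section 6.5 and the synopsis conflicts with Sections 11.2 and 13.2 for ketoconazole and itraconazole, and the neighbouring azole rules need reconciling

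*Combined protocol and SAP*

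**What the plan says.** The dose without an interacting drug is in Section 6.5: "Ibrutinib will be administered at a dose of 420 mg by mouth once a day". The same section then gives the azole rule, "For patients on azoles, the starting dose will be 140 mg by mouth once a day", and the synopsis repeats it: "Patients on azoles will start ibrutinib at a dose of 140 mg by mouth once a day". Neither sentence names an agent or refers to another section. The sentence that follows in both places does: "Patients using Posaconazole as outlined in section 11.2 will start ibrutinib at a dose of 70 mg by mouth once a day".

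Section 11.2 is more specific. Its text ties the 140 mg dose to "fluconazole, voriconazole or lower doses of posaconazole as outlined in the table below", and gives 70 mg with higher-dose posaconazole. Its table assigns 140 mg to moderate inhibitors, voriconazole 200 mg twice daily and lower-dose posaconazole, and 70 mg to higher-dose posaconazole. For all other strong CYP3A inhibitors the table reads "Avoid concomitant use. If these inhibitors will be used short-term", and it then calls for ibrutinib to be interrupted.

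Section 13.2 lists strong inhibitors, beginning with ketoconazole, in a sentence that ends: "saquinavir, clarithromycin, telithromycin, itraconazole, nefazodone, and cobicistat) should be avoided". It allows voriconazole and posaconazole with the Section 11.2 modifications. It also names both, with ketoconazole and itraconazole, among strong inhibitors for which, in courses of 7 days or less, sites should "consider interrupting IMBRUVICA therapy during the duration of inhibitor use". The Section 11.2 text gives similar advice for short-term antifungals that are strong inhibitors.

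Section 10 excludes, before ibrutinib starts, patients who require chronic treatment with strong CYP3A inhibitors.

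**The concern.** Ketoconazole and itraconazole are azoles. A site that takes the first dose from Section 6.5 or the synopsis finds 140 mg for a patient on either drug. A site that reads Section 13.2 or the Section 11.2 table finds that the combination is to be avoided, or ibrutinib interrupted. Two sites could both follow the protocol and treat the same patient differently.

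This bears on safety and tolerability, which is a secondary objective. It also affects reporting. Section 6.6 counts any dose above the one the protocol specifies as an overdose. Where one passage specifies 140 mg and another specifies interruption, it is unclear whether a 140 mg dose is an overdose.

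**Working it through.** No sample size or test is involved, so the main check sets the passages side by side.

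| Co-medication | Section 6.5 and synopsis | Section 11.2 text | Section 11.2 table | Section 13.2 | Result |
|---|---|---|---|---|---|
| Fluconazole | 140 mg | 140 mg | 140 mg (moderate inhibitor) | not named | agree |
| Voriconazole 200 mg twice daily | 140 mg | 140 mg | 140 mg | allowed, per 11.2 | start dose agrees |
| Voriconazole, other doses | 140 mg | 140 mg, if the reference to the table does not qualify voriconazole | not listed by name | allowed, per 11.2 | unclear |
| Posaconazole, lower doses | per 11.2 | 140 mg | 140 mg | allowed, per 11.2 | agree once read with 11.2 |
| Posaconazole, higher doses | 70 mg | 70 mg | 70 mg | allowed, per 11.2 | agree |
| Ketoconazole, itraconazole | 140 mg | not named; short courses of strong inhibitors: consider interrupting | other strong inhibitors: avoid, or interrupt ibrutinib if short-term | avoid; short courses: consider interrupting | conflict |

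The last row is the hard conflict. Three softer points remain.

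1. **Voriconazole dose.** The Section 11.2 text can be read as giving 140 mg with voriconazole at any dose. The table lists 200 mg twice daily only.
2. **Courses of 7 days or less.** For voriconazole and posaconazole, Sections 11.2 and 13.2 say to consider interrupting ibrutinib, and Section 11.2 also gives a reduced dose. Nothing says when each applies.
3. **Exclusion.** Section 13.2 gives voriconazole and posaconazole as examples of strong inhibitors. Section 10 excludes patients needing chronic strong inhibitors, yet Section 11.2 sets doses for patients on these drugs and expects most patients to be on azoles until day 100. Chronic is not defined.

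The only interaction size given for an inhibitor is in Section 13.2: ketoconazole raised ibrutinib AUC 24-fold and Cmax 29-fold in healthy volunteers. These are cited results and cannot be re-derived from the documents. To show scale, assume that exposure is proportional to dose, which the documents do not state:

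relative exposure = fold increase x (dose given / 420 mg)

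- AUC at 140 mg: 24 x 140/420 = 8.0 times that of 420 mg alone.
- Cmax at 140 mg: 29 x 140/420 = 9.7 times.
- If the increase is read as added to baseline: AUC 25 x 140/420 = 8.3 times; Cmax 30 x 140/420 = 10.0 times.

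For comparison, a cut from 420 to 140 mg offsets a rise of 420/140 = 3-fold.

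**The case against.** The strongest reply is that the intent can be worked out. Section 16 sends readers to the dose modification section for dosing with azoles. The dose-level list in Section 11.1 ties the 140 mg start to azole use as described in Section 11.2. Section 13.2 sends voriconazole and posaconazole back to Section 11.2. For every azole that Section 11.2 expects, apart from voriconazole at doses the table does not list, the start doses agree. To give ketoconazole with 140 mg, a site would have to disregard two avoidance statements and, if use were chronic, an exclusion criterion that the coordinating center rechecks before ibrutinib starts. The short-course advice says only to consider interrupting, and it appears in both Section 11.2 and Section 13.2, so those sections are not opposed on it. The reference to the table in the Section 11.2 text may also qualify voriconazole, which would remove the first softer point.

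Most of this stands, and it limits the reach of the problem. It does not remove the conflict. The azole sentences in Section 6.5 and the synopsis carry no cross-reference, and the posaconazole sentence says nothing about ketoconazole or itraconazole. The pointers to Section 11.2 also leave open which instruction applies to short courses.

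**Conclusion.** The contradiction is real and narrow. Section 6.5 and the synopsis, taken as written, set 140 mg with two azoles that Section 13.2 says to avoid and that the Section 11.2 table places under avoid or interrupt. The voriconazole, short-course and exclusion points are ambiguities rather than direct contradictions.

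A reader might infer three stronger things that the documents do not support.

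- **Every patient on an azole gets 140 mg.** Both places set 70 mg for posaconazole as described in Section 11.2.
- **Most patients are affected, because most are expected to be on azoles until day 100.** That expectation names fluconazole, voriconazole and lower-dose posaconazole. No passage expects ketoconazole or itraconazole.
- **Azole use brings up to an 8-fold excess.** The figure is 8.0 times the reference AUC, that is 7-fold above it. It applies to ketoconazole only and rests on dose proportionality. It is not a ceiling, since Cmax gives 9.7 times. The documents give no interaction size for any other azole.

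**What to change.** Reconcile the synopsis and Sections 6.5, 10, 11.1 (dose levels), 11.2 (text and table) and 13.2. In Section 6.5 and the synopsis, replace the unqualified word azoles with a cross-reference to one reconciled instruction by agent. State which passage takes precedence, including for courses of 7 days or less and for voriconazole doses that the table does not list. Make clear how the exclusion of chronic strong inhibitors applies to patients on continuing voriconazole or posaconazole.

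The sponsor decides the instruction for each agent; this review proposes none. The cost is a wording amendment, with no extra data and no change to the sample size.
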